2.4.4.4 Multiplicity issues

To control the family-wise type I error, a hierarchical testing procedure will be applied.

For the primary efficacy endpoint (change from Baseline to Week 26 in HbA1c), the hypotheses of statistical superiority of sotagliflozin versus placebo will be tested at 2-sided 5% significance level in the following population and order. The testing will stop as soon as the endpoint is found to be not statistically significant at $\alpha=0.05$ (2 sided).

- Comparing sotagliflozin 400 mg versus placebo, in:
 - The overall patient population (ie, patients in stratum CKD3A and stratum CKD3B),
 - Patients in stratum CKD3A,
 - Patients in stratum CKD3B.
- Comparing sotagliflozin 200 mg versus placebo, in:
 - The overall patient population (ie, patients in stratum CKD3A and stratum CKD3B),
 - Patients in stratum CKD3A,
 - Patients in stratum CKD3B.

Once the primary variable (change from Baseline to Week 26 in HbA1c) is statistically significant at $\alpha=0.05$ (2-sided) in all 6 populations in the order above, the following secondary efficacy variables will be tested in the overall population by the following prioritized order. The testing will stop as soon as an endpoint is found to be not statistically significant at $\alpha=0.05$ (2 sided).

- Comparing sotagliflozin 400 mg versus placebo, in:
 - Change from Baseline to Week 26 in FPG,
 - Change from Baseline to Week 26 in body weight,
 - Change from Baseline to Week 12 in SBP for patients with Baseline SBP ≥ 130 mmHg,
 - Change from Baseline to Week 12 in SBP for all patients,
 - Proportion of patients with HbA1c $< 7.0\%$ at Week 26.
- Comparing sotagliflozin 200 mg versus placebo, in:
 - Change from Baseline to Week 26 in FPG,
 - Change from Baseline to Week 26 in body weight,
 - Change from Baseline to Week 12 in SBP for patients with baseline SBP ≥ 130 mmHg.

Once the above secondary variables are statistically significant at $\alpha=0.05$ (2-sided), Hochberg's step-up procedure (1) will be performed to test the remaining 4 secondary variables: order a number of m ($m=4$ here) tests by p-values (from lowest to highest) $P_{(1)} \dots, P_{(m)}$ associated with tests $H_{(1)} \dots, H_{(m)}$, find the largest k (called R) so that, for all $k=1, \dots, R$, $P_{(k)} \leq \alpha / (m+1-k)$, conclude $H_{(1)} \dots, H_{(R)}$ statistically significant.

- Percentage change in UACR from Baseline to Week 26 for patients with UACR > 30 mg/g at Baseline, comparing sotagliflozin 400 mg and 200 mg, respectively, versus placebo.
- Proportion of patients with HbA1c $< 7.0\%$ at Week 26, comparing sotagliflozin 200 mg versus placebo.
- Change from Baseline to Week 12 in SBP for all patients comparing sotagliflozin 200 mg versus placebo.

No multiplicity adjustment will be made on efficacy variables other than those mentioned above.

In addition, no further multiplicity adjustment (split of alpha) is needed for multiple analyses (ie, first step and second step analyses see [Section 3](#)). The results of the first step analysis will not be used to change the conduct of the ongoing study in any aspect and all primary and secondary efficacy endpoints will be fully evaluable at the time of the first step analysis. Analyses beyond Week 26 will be descriptive.

2.4.5 Analyses of safety data

The summary of safety results will be presented by treatment group. The safety data will be summarized for the 26-week core treatment period and the 52-week entire treatment period separately, unless otherwise specified.

The observation period defined in [Section 2.1.4](#) is applicable in all safety analyses for classification of AEs, determination of treatment-emergent Potentially Clinically Significant Abnormality (PCSA) values and the last on-treatment value for laboratory, vital sign, BMD and ECG.

General common rules

All safety analyses will be performed on the safety population as defined in [Section 2.3.2](#), unless otherwise specified, using the following common rules:

- Safety data in patients who do not belong to the safety population (eg, exposed but not randomized) will be listed separately.
- The baseline value (with the exception of serum creatinine and eGFR) is defined as the last available value before the first dose of double-blind IMP. For creatinine and eGFR, the baseline value is defined as the average of all values before the first dose of double-blind IMP.
- PCSA values are defined as abnormal values considered medically important by the Sponsor according to predefined criteria/thresholds based on literature review and defined by the Sponsor for clinical laboratory tests, vital signs, and ECG ([Appendix A](#)).
- PCSA criteria will determine which patients had at least 1 PCSA during the TEAE period, taking into account all evaluations performed during the TEAE period, including nonscheduled or repeated evaluations. The number of all such patients will be the numerator for the treatment-emergent PCSA percentage.
- The treatment-emergent PCSA denominator by group for a given parameter will be based on the number of patients assessed for that given parameter in the TEAE period by treatment group on the safety population.
- For laboratory parameters cited in the protocol as efficacy endpoints (eg, HbA1c, plasma glucose, etc.), PCSA summaries will not be provided. These parameters will be summarized in efficacy [Section 2.4.4](#).
- For quantitative safety parameters based on central laboratory/reading measurements, descriptive statistics will be used to summarize results and change from baseline values by visit and treatment group for the 52-week entire treatment period only. Summaries will include the last on-treatment value. The last on-treatment value is commonly defined as the value collected at the same day/time of the last administration of IMP for the 52-week entire treatment period. If this value is missing, this last on-treatment value will be the closest value prior to the last administration of IMP during the 52-week entire treatment period.

- The analysis of the safety variables will be essentially descriptive and no systematic testing is planned. Relative risks versus placebo and their 95% confidence intervals may be provided, if relevant.
- Selected safety analyses will be summarized by age, gender, racial subgroups, and any pertinent subgroups (see details in [Section 2.4.5.1](#) and [Section 2.4.5.2](#)).

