### **9.2.1.7 Bone Mineral Density**

Bone mineral density of femoral neck, lumbar spine and total hip will be assessed in all patients at Baseline (Week 0, Day 1  $\pm$ 7 days) and at Visit 11 (Week 52, Day 364  $\pm$ 7 days) using dual-energy X-ray absorptiometry (DEXA). Bone mineral density assessments will be performed locally with central reading. All DEXA scans will be retained as source data.

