## 10 STUDY PROCEDURES

### 10.1 VISIT SCHEDULE

The visit schedule and procedures/assessments are listed in the Study Flow Chart ([Section 1.2](#)). The aim of this section is to provide details on how some of the procedures/assessments should be performed.

This is an out-patient study and consists of 12 on-site visits, although optional on-site and/or telephone visits can be scheduled at any time for any reason during the study whenever considered necessary by the Investigator.

The patients need to be fasting for on-site visits Visit 1 through Visit 11 (Week -4 through Week 52), unless instructed otherwise by the Investigator. Throughout the study, “fasting” is defined as 8 hours without food. **Note:** If the patient is not fasting at the visits specified above, the blood sample will not be collected and a new appointment should be given to the patient for the following day if possible, with instruction to be fasted (other procedures can be performed as scheduled). All laboratory assessments will occur prior to IMP administration on the day of the visit.

The Run-in visit (Visit 2) can be performed as soon as the results of all Screening tests are available and the patient is confirmed to be eligible for participation in the study. The visit window for on-treatment Visit 4 through Visit 11 should occur at the schedule  $\pm 5$  days. Visit 11 (EOT) should occur during Day 364 to 369. For the Follow-up (Visit 12), the visit window should occur within  $\pm 5$  days, 4 weeks after last dose of IMP.

If one visit date is changed, the next visit should occur according to the original schedule, ie, calculated from the date of Baseline visit (Visit 3, Week 0).

For a complete list of procedures scheduled for each study visit please refer to the Study Flow Chart ([Section 1.2](#)), which details the procedures to be performed.

All data obtained during the study visits are reviewed by the Investigator and Sub-Investigators who are qualified in treatment of T2D and are trained on the study.

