#### **10.1.3.2 On-site visit at Week 52 (Visit 11) – End of Treatment**

The following procedures will be performed at this visit:

- Concomitant medications are assessed.
- Measurement of body weight.
- Complete physical examination. Vital signs. After 5 minutes resting, seated SBP, DBP, and HR will be assessed 3 times with at least 1 minute between each measurement (see [Appendix C](#) for details).
- IMP accountability and compliance for double-blind IMP.
- IRT to be notified.
- AEs/SAEs/AESI/EOSI and hypoglycemia (if any) are reported.
- Patients evaluated for glycemic rescue (see [Section 8.2.1](#)).
- Evaluate for 50% increase in creatinine.
- Patient diary is collected and reviewed and a new one is dispensed. Instructions/training are provided as needed.
- Fasting SMBG is assessed.
- 12-lead ECG.
- The following laboratory testing (by the central laboratory):
  - FPG
  - HbA1c
  - Urine pregnancy testing for WOCBP
  - Clinical chemistry (including amylase, lipase, fasting lipids, and uric acid) and hematology
  - Cystatin C
  - Fructosamine
  - NT-proBNP
  - Urinalysis (dipstick and microscopy)
  - Urine albumin, calcium, phosphorus, glucose, and creatinine

- Collection of home urine for analysis of albumin, creatinine, calcium, phosphorus, magnesium, glucose, and albumin creatinine ratio.
- Additional laboratory testing at this visit:
  - Markers of intestinal transit and absorption (vitamins B6, B12, K, E, and A, serum folate, and ferritin)
  - Markers of bone and calcium metabolism: serum calcium (adjusted for creatinine), serum 25 hydroxyvitamin D, serum 1,25-dihydroxyvitamin D, serum phosphorus (adjusted for phosphorus), serum magnesium, serum iPTH, markers of bone resorption (serum NTX, serum  $\beta$ -CTX-1) and bone formation (serum P1NP and osteocalcin), and serum ALP.
- Pre-dose PK (plasma concentration sample for sotagliflozin and sotagliflozin-3-O-glucuronide); an additional blood sample will be collected 3 hours after IMP administration for the assessment of creatinine (for eGFR) and for assessing plasma concentration of sotagliflozin and sotagliflozin-3-O-glucuronide.
- Assessment of BMD in all patients. BMD will be assessed locally (with central reading) on Day 364, with a window of  $\pm 7$  days for this assessment.
- Patients are instructed to return to the site in the fasting state for Visit 12 (Week 56).

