2.1.4.7 Electrocardiogram variables

12-lead ECG will be performed at Visit 2/Run-in, Visit 9/Week 26, and Visit 11/Week 52. ECG status of “Normal” or “Abnormal” will be reported in the e-CRF as determined by the Investigator.

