- m The markers of intestinal transit and absorption include vitamins B6, B12, K, E, and A, serum folate, and ferritin.
- n Markers of bone and calcium metabolism include: serum calcium, serum 25-hydroxyvitamin D, serum 1,25-dihydroxyvitamin D, serum phosphorus, serum magnesium, serum parathyroid hormone (iPTH), markers of bone resorption (serum NTX, serum β -CTX-1), bone formation (serum P1NP and osteocalcin) and serum alkaline phosphatase.
- o Urinalysis includes urine dipstick and microscopy. Dipstick includes assessment of specific gravity, pH, protein, blood, ketones, bilirubin, urobilinogen, nitrite, and leukocyte esterase. Microscopy includes, but is not limited to, detection of formed cellular elements, casts, bacteria, yeast, parasites, and crystals in centrifuged urine sediment. In the event of abnormal urinalysis findings suspicious of urinary tract infection (UTI), urine culture should be performed. Positive urine culture determination will be based upon the criteria of the reporting laboratory. Additionally, urine culture should be performed if at any point the Principal Investigator suspects the presence of a UTI.
- p BMD will be assessed locally (with central reading) in all patients at Baseline (Week 0, Day 1 ± 7 days) and at Visit 11 (Week 52, Day 364 ± 7 days).
- q Patients will collect overnight urine on Weeks 0, 2, 4, 12, 26, and 52. In the night prior to the visits, the urine before sleep will be discarded and the urine during sleep and the first morning urine (after getting up) will be collected. The visits should be rescheduled to allow for urine collection in case a patient missed it. Urinary albumin, total protein, creatinine, calcium (adjusted for creatinine), phosphorus (adjusted for serum phosphorus and creatinine), magnesium (adjusted for serum magnesium and urinary creatinine), and glucose will be assessed.
- t The 50% increase will be from Baseline value (to Week 8) or from the arithmetic mean of creatinine values from last two visits (after Week 8) only at visits having a measurement of creatinine.

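### The generic last on-treatment rule in SAP 2.4.5 is extended to bone mineral density, where a permitted Week 52 scan after the last dose leaves that one row empty or filled with the baseline scan

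*SAP*

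**What the plan says.** The opening of SAP 2.4.5 applies its observation periods to several items, among them "the last on-treatment value for laboratory, vital sign, BMD and ECG". The matching list in Protocol 11.4.3 covers laboratory, vital sign and ECG parameters but not BMD.

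The general rules in SAP 2.4.5 then set the scope: "For quantitative safety parameters based on central laboratory/reading measurements, descriptive statistics will be used to summarize results and change from baseline values by visit". These summaries are to include the last on-treatment value. BMD falls within that scope, because under Protocol 9.2.1.7 "Bone mineral density assessments will be performed locally with central reading". ECG is a different case: its normal or abnormal status "will be reported in the e-CRF as determined by the Investigator".

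The last on-treatment value is the one from the day of the last dose. The fallback reads: "If this value is missing, this last on-treatment value will be the closest value prior to the last administration of IMP". Nothing there requires the chosen value to be post-baseline.

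SAP 2.4.5.8 plans the BMD summary at Week 52 from all scans obtained in the study, whether or not treatment had stopped. It does not mention a last on-treatment row.

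**The concern.** The rule suits parameters measured repeatedly during treatment, where an earlier on-drug value is nearly always available. BMD has two scheduled scans a year apart. If the second scan falls after the last dose, the only scheduled scan left is the baseline one.

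Protocol 9.5 gives possible effects on bone and calcium metabolism as the reason for scanning every patient. A row meant to show BMD at the end of treatment should not drop compliant completers or record a change of exactly zero because of when the scan was booked. A built-in zero pulls the row towards no change, which is the unhelpful direction for a safety summary. The row could then disagree with the Week 52 row for the same patients.

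**Working it through.** The plan gives no figure to reproduce here. The check is a day count and a reading of the rules together.

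**Inputs**
- Scheduled scans: Week 0 and Week 52 only (SAP 2.1.4.8).
- Scan windows (SAP Appendix E, footnote p): "in all patients at Baseline (Week 0, Day 1 ± 7 days) and at Visit 11 (Week 52, Day 364 ± 7 days".
- End-of-treatment visit (Protocol 10.1): "Visit 11 (EOT) should occur during Day 364 to 369".
- Dosing at that visit is inferred from Protocol 10.1.3.2: "an additional blood sample will be collected 3 hours after IMP administration for the assessment of creatinine".
- Treatment epoch: first dose to last dose (SAP 2.1.4).
- BMD baseline: a pre-dose scan or, failing that, the closest one within a month after the first dose (SAP 2.5.4).
- Protocol on-treatment period: up to 10 days after the last dose (Protocol 9.2).

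**Step 1. Permitted Week 52 scan days.** 364 − 7 = 357 and 364 + 7 = 371, so 371 − 357 + 1 = 15 days.

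**Step 2. Permitted days after the last dose.**

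| Last dose | Later permitted scan days | Count | Share of window |
|---|---|---|---|
| Day 364 | 365 to 371 | 371 − 364 = 7 | 7/15 = 47% |
| Day 369 | 370 to 371 | 371 − 369 = 2 | 2/15 = 13% |

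These are shares of calendar days, not of patients.

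**Step 3. What the row takes for a completer scanned on one of those days.** The Week 52 scan is neither on nor before the last-dose day, so it cannot be used. I read the fallback as limited to values within the treatment period.
- Baseline scan before Day 1: there is no scan in the treatment period, so the row has no value.
- Baseline scan after Day 1 (the flow chart allows up to Day 1 + 7 = Day 8): that scan lies inside the treatment epoch and is the closest earlier value. It is then both the baseline and the last on-treatment value, so the change is 0.

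Example: only baseline scan on Day 5, last dose on Day 364, Week 52 scan on Day 368. The Week 52 row reports the Day 368 value minus the Day 5 value. The last on-treatment row reports the Day 5 value minus itself, which is 0.

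**Step 4. Patients who stop early.** Protocol 10.3.3 moves the end-of-treatment assessments to a Premature EOT Visit, preferably before stopping and otherwise as soon as possible afterwards. Protocol 10.1.3.2 lists BMD among those assessments, although with a Day 364 window, so an early scan is an inference. A scan taken shortly after stopping is excluded from the row in the same way.

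**Step 5. Would the protocol period cover the late scans?** For completers the longest gap in Step 2 is 371 − 364 = 7 days, which is within 10. All of these scans fall inside the protocol's on-treatment period.

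**The case against.** The strongest reply is that the BMD-specific section governs. SAP 2.4.5.4 and 2.4.5.5 name the last on-treatment value for laboratory and vital-sign summaries, and 2.4.5.8 does not for BMD. The separate definition in SAP 2.5.4 is also headed for laboratory variables and vital signs. On that reading the row may never be produced. The zero change also needs a programmer to pick a record already used as baseline, and a post-dose scan becomes baseline only when no pre-dose scan exists.

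Much of this stands. A reader might infer that a late Week 52 scan is lost from the BMD analysis. The documents do not support that: 2.4.5.8 keeps it in the Week 52 summary, which is also the only BMD analysis in Protocol 11.4.3.8. A reader might also turn the day counts into a percentage attenuation of the mean change. That would need the distribution of scan days, which is not given. Nor does the point carry over to laboratory values or vital signs. For those the SAP rule is a defensible convention, and values in the treatment-emergent period still count in the abnormality tables.

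What does not stand is that nothing needs correcting. SAP 2.4.5 names BMD expressly, 2.4.5.8 neither removes nor redefines the row, and no rule bars the baseline record. A programmer following 2.4.5 literally would produce the row as described.

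**Conclusion.** The point holds as a minor error confined to one descriptive row. For BMD, the stated rule cannot use a compliant Week 52 scan done after the last dose, and it yields no value or a change of 0 instead. This applies to 7 of 15 permitted scan days with a Day 364 last dose and 2 of 15 with a Day 369 last dose. A Premature EOT scan done soon after stopping is excluded in the same way. The Week 52 BMD summary, all hypothesis tests and all efficacy results are unaffected.

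The conclusion assumes that the last dose is taken at Visit 11, that the row is produced as 2.4.5 directs, and, for the zero, that no post-baseline condition is added in programming. The number of patients affected is unknown. If every final scan was done on or before the last-dose day, the effect is zero.

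**What to change.** In SAP 2.4.5, add one sentence: for BMD, the last on-treatment value is the last post-baseline scan up to 10 days after the last dose, and it is never the scan used as baseline. This borrows the on-treatment period in Protocol 9.2, which Protocol 11.4.3 already applies to last on-treatment values for other parameters. It also retains a Premature EOT scan done within those 10 days, which is why I prefer it.

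The alternative is to delete BMD from the list in 2.4.5 and state that 2.4.5.8 governs BMD. That is simpler, but it gives up a last on-treatment row that could be informative for patients who stop early.

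The cost of the preferred option is one sentence, one derivation flag and one entry in SAP 1.6, with no new data. SAP 1.6 records that the first-step analysis had already been reported for top-line results, so the entry should be dated and labelled a clarification. No change to the laboratory or vital-sign rules is needed.

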2.4.5.1 Analyses of hypoglycemia

Analyses of hypoglycemia will be performed on the TEAE period as defined in [Section 2.1.4](#). Hypoglycemia will be classified as severe hypoglycemia, documented symptomatic hypoglycemia, asymptomatic hypoglycemia, probable symptomatic hypoglycemia or relative hypoglycemia (See [Section 2.1.4.1](#)).

The number (%) of patients with 1) any hypoglycemia, 2) severe hypoglycemia and documented symptomatic hypoglycemia will be summarized respectively by treatment group during the TEAE period, as well as the incidence rate in patient years. Two types of incidence rates will be presented: the number of patients with event(s) per 100 patient-years (calculated as the number of patients with at least 1 event/ total exposure in 100 patient-years) and the total number of events per 100 patient-years (calculated as the total number of events / total exposure in 100 patient-years). Note: here exposure in days is duration of treatment-emergent AE period, ie, duration of IMP treatment in days +1 ([Section 2.1.4](#)).

The summary of frequency and incidence rate in patient-years for severe hypoglycemia or documented symptomatic hypoglycemia will be provided as appropriate by gender, age group (<50, ≥50 to <65, ≥65 years), race (White, Black or African American, Asian, Other), baseline eGFR category, prior antidiabetic medication (No antidiabetic therapy, Insulin [alone or with other antihyperglycemic agents], SU and/or glinide [alone or with other non-insulin antihyperglycemic agents], Other [non-insulin antihyperglycemic agents except SU and glinide]).

A KM curve will be provided by treatment group for the time to first severe hypoglycemia or documented symptomatic hypoglycemia during the TEAE period for the 52-week entire treatment period only (see [Section 2.5.4](#)).

Documented symptomatic hypoglycemia may be presented by ≤ 70 mg/dL (3.9 mmol/L) and < 54 mg/dL (3.0 mmol/L) respectively, as appropriate.

A listing of patients for all events reported on the dedicated e-CRF “Hypoglycemic event information” page will be provided with each category flagged (ie, severe hypoglycemia, documented symptomatic hypoglycemia, asymptomatic hypoglycemia, probable symptomatic hypoglycemia and relative hypoglycemia).

